7.2.1 Pre-randomisation evaluations

These evaluations occur prior to the patient receiving any study intervention.

Run-in – Screening period: V1 (day -28→-8)

A signed Informed Consent Form and, when applicable, an Assent Form will be obtained before any other study-specific assessments are performed.

Informed Consent Form and Assent Form will be collected at V1, being this visit performed between day -28 and day -8.

Between day -28 and day -8 the following screening assessments will be performed and collected:

- Demographic characteristics
- Pregnancy test
- Clinical physical examination
- Medical history and current medical conditions
- Vital signs
- Liver function history
- Heart function history
- Serum Ferritin
- ECG
- Urinalysis
- Renal function
- Hepatitis serology
- Haematology/Biochemistry
- Body height/weight

Platelet count, neutrophil count, haemoglobin and serum creatinine must be assessed between day -9 and day -8 or, alternatively, at day -7 at the wash-out visit (V2).

Additional information regarding clinical procedures will be provided in the SPM.

Run-in – Screening period: Wash-out visit V2 (day -7)

V2 will be performed at day -7. This visit is meant to assess the patient for inclusion/exclusion criteria on the basis of the examinations/evaluations performed during the screening period. Platelet count, neutrophil count, haemoglobin and serum creatinine, if not assessed at day -9 or day -8 of the screening period, must be evaluated at the time of this visit (V2, day -7).

CONFIDENTIAL

DEEP Consortium
DEEP2-Efficacy/Safety Study Protocol

Protocol No. DEEP-2

During this visit patients will be also required to suspend any ongoing chelation treatment from day -6 to day -1.

Additional information regarding clinical procedures will be provided in the SPM.

Run-in: Wash-out period (day -6→-1)

Patients are required to suspend any ongoing chelation treatment from 00.00 hrs of day -6 to day -1. Chelation naïve patients will not respect the same time period before starting treatment and the wash-out phase is not foreseen. No visits are foreseen in this period.

Baseline (Study Entry): V3 (Day 0)

This visit will be completed 6 days after any ongoing chelation treatment has been withdrawn (wash-out).

The study intervention (DFP or DFX) will be assigned to the patients according to randomisation.

The following assessments will be performed before trial treatment administration:

- Randomisation
- Clinical physical examination
- Vital signs
- Liver MRI
- Serum Ferritin
- ECG
- Cardiac MRI T2*
- Urinalysis
- Renal function
- Haemoglobin
- Neutrophil count
- Haematology/Biochemistry
- Concomitant medications
- Medical events (as events occurred after the signature of the Informed consent)
- Body height/weight
- Ocular examination
- Audiometric examination
- Pubertal staging (according to Tanner, see **Section 10.1**)
- CHQ

Liver MRI and cardiac MRI T2* are allowed to be executed at day 0 ± 20 days.

At the completion of the evaluation, the patient will be randomised to one of the two study treatments and is provided with the assigned intervention (sufficient for one-month treatment) and instructions for dose preparation and administration. DFP and DFX treatments must start at day 0.

Additional information regarding clinical procedures will be provided in the SPM.

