5.1 Inclusion criteria

Patients will be eligible for inclusion in this study if the following criteria apply:

- patients of both genders aged from 1 month up to less than 18 years at the time of enrolment
- patients affected by any hereditary haemoglobinopathy requiring chronic transfusion therapy and chelation, including but not limited to thalassemia syndromes and sickle cell disease
- patients
 - on current treatment with DFO or DFX or DFP in a chronic transfusion program receiving at least 150 mL/kg/year of packed red blood cells (corresponding approximately to 12 transfusions)
 - naïve to chelation treatment who have received at least 150 mL/kg of packed red blood cells (corresponding to approximately 12 transfusions) in a chronic transfusion program and with serum ferritin levels \geq 800 ng/mL at screening
- Until availability of results from the PK Study (Study DEEP-1, EudraCT n. 2012-000658-67) for patients aged from 1 month to less than 6 years: known intolerance or contraindication to DFO
- written informed consent obtained from patient's legal guardian in accordance with the national legislations. Patient's informed assent will be collected according to his/her maturity and understanding.

5.2Exclusion criteria

A patient will not be eligible for inclusion in this study if any of the following criteria apply:

- patients with known intolerance or contraindication to either DFP or DFX
- patients receiving DFX at a dose > 40 mg/kg/day or DFP at a dose > 100 mg/kg/day at screening
- platelet count <100.000/mm³ at the wash-out visit (day -7)
- absolute neutrophil count <1.500/mm³ at the wash-out visit (day -7)
- Hb levels lower than 8g/dL at the wash-out visit (day -7)
- Evidence of abnormal liver function (ALT level >5xULN) at screening
- iron overload from causes other than trasfusional haemosiderosis
- severe heart dysfunction secondary to iron overload defined as the occurrence of heart failure or severe arrhythmia or cardiac MRI T2* lower than 10 ms available
- serum creatinine level > ULN for age at the wash-out visit (day -7)
- history of significant medical or psychiatric disorder
- the patient has received another investigational drug within 30 days prior to consent to study participation
- fever and other signs/symptoms of infection at the wash-out visit (day -7)
- concomitant use of trivalent cation-dependent medicinal products such as aluminium-based antacids
- positive test for β-HCG or lactating female patients.

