The clinical assessments will be conducted at each scheduled visit. The timing of each visit is listed in **Table 5**. Each visit will be scheduled at the same day of the month \pm 7 days. MRI evaluations (cardiac and hepatic) will be allowed \pm 20 days deviation from the scheduled visit.

Further information is provided in the following sections and detailed procedures for conducting each assessment are provided in the Study Procedures Manual (SPM).

At each visit, following completion of all procedures, the patient will be discharged from the unit.

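### The baseline MRI window runs to day +20, after open-label allocation and first dose, so a T2* baseline can be on treatment and whether it exists can depend on the known arm

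*Combined protocol and SAP*

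**What the plan says.** Section 7.2.1 is headed as pre-randomisation evaluations and opens with "These evaluations occur prior to the patient receiving any study intervention". For the baseline visit (V3, day 0) it adds "The following assessments will be performed before trial treatment administration", and the list that follows includes liver MRI and cardiac MRI T2*. The order is then stated: "At the completion of the evaluation, the patient will be randomised to one of the two study treatments", and "DFP and DFX treatments must start at day 0".

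Between the list and those last two statements stands "Liver MRI and cardiac MRI T2* are allowed to be executed at day 0", with a tolerance of 20 days either side. The same tolerance is given in Section 7.2 ("MRI evaluations (cardiac and hepatic) will be allowed", 20 days either side of the scheduled visit, with no exception for V3), in footnotes 3 and 4 of Table 5, and in Sections 7.3.11 and 7.3.14.

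The rules that use the scan are these:
- Section 6.5: the trial is not blinded.
- Section 4.3: children aged 10 or over need both criterion A (ferritin) and criterion B (T2*). Those who would need sedation for the scan are judged on ferritin alone.
- Section 4.3.1: criterion B is a percentage change from baseline T2*, with cut-offs at 10% and 20 ms.
- Section 11.2: PP1, the primary analysis set, requires the composite at baseline and at one year.
- Section 11.6: in the ITT analysis, a missing MRI at either time makes the child a treatment failure.

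**The concern.** A site can keep to the 20-day tolerance and still break the pre-dose rule. The plan does not say which rule prevails, or whether a post-dose baseline scan counts as a major violation for PP1.

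Two consequences follow. First, the reference value for criterion B may already contain some effect of the assigned drug. Second, in an open-label trial any assessment that may follow allocation may be obtained, postponed or declined with the arm known. For a child aged 10 or over who goes on to complete the year, a missing baseline scan removes the child from PP1 and makes the child an ITT failure. If the child is instead classed as needing sedation, the endpoint becomes ferritin alone. No section requires that classification before allocation; Section 6.6 stratifies by age only. An event after randomisation can thus change the analysis set, the outcome or the endpoint definition.

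**Working it through.** **The plan's own figure.** This point disputes no sample-size figure. With 65% (DFX), 67.5% (DFP), margin 12.5 points, one-sided 0.025 and 80% power (Section 11.12), n per arm = (1.960 + 0.842)² × (0.65×0.35 + 0.675×0.325) / 0.15² ≈ 156. That is 312 in total against 310 stated. Power at 155 per arm is 79.8%, and 310/0.8 gives 388 enrolled. Moving the scan changes none of these.

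**Dates.** Take day 0 as first dose and month 12 as day 365.
- Latest permitted baseline: day +20, after 20/365 = 5.5% of the treatment year.
- Shortest interval to the final scan: 345 − 20 = 325 days. Longest: 385 + 20 = 405 days.
- With the baseline confined to day −20 to day 0, the interval is 345 to 405 days.

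**Size of the on-treatment effect (assumes linear T2* change).** For a true annual gain g, the day +20 baseline is 1 + g×20/365 of the day-0 value. With g = 10%:
- Baseline factor: 1.0055, a shift of about 0.5%.
- Read at day 365: 1.10/1.0055 − 1 = 9.4%.
- Read at day 345: (1 + 0.10×345/365)/1.0055 − 1 = 8.9%.
- For comparison, a day-0 baseline with a final scan at day 345 reads 10% × 345/365 = 9.45%.

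For a day +20 baseline to show the 10% rise required when baseline T2* is below 20 ms, the true annual gain must be 0.10/(1 − 1.1×20/365) = 10.6% with a final scan at day 365, or 0.10/(345/365 − 1.1×20/365) = 11.3% at day 345. Only children in those narrow bands change from success to failure.

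**Sensitivity to allocation-dependent missing scans (shares assumed; the documents give none).** Take the ITT analysis with 194 per arm. Let a share m of one arm complete the year without a baseline scan, unrelated to their true response, and score them as failures, so that p becomes p(1 − m). Other dropouts are ignored. The chance of claiming non-inferiority is Φ[(p1 − p2 + 0.125)/SE − 1.96].

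| Setting | Missing share | Result |
|---|---|---|
| True rates at the margin: DFP 52.5%, DFX 65% | none | one-sided error 2.5% |
| same | 2% in DFX only | 4.5% |
| same | 5% in DFX only | 9.5% |
| same | 10% in DFX only | 25% |
| Planned rates: DFP 67.5%, DFX 65% | none | power 88% |
| same | 5% in both arms | power 86% |
| same | 5% in DFP only | power 67% |

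The imbalance drives the result. These shares are of the whole arm, but only children due a cardiac scan can contribute. If 60 to 70% of an arm were scanned (an assumption, borrowing the level at which Section 11.6 would test T2* formally), 5% of the arm would be 5/0.70 = 7.1% to 5/0.60 = 8.3% of those children.

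**The case against.** The tolerance looks like a deliberate scheduling allowance: Section 7.3.21 gives the same 20 days to ocular and audiometric tests, and some children must travel to another MRI centre. It also permits scans before day 0, so a post-dose baseline is allowed but not required. Section 11.13 expects negligible missing data, T2* images are analysed centrally (Section 7.3.14), and the ITT analysis only corroborates PP1. All of this stands and limits the size. None of it removes the conflict, and central analysis does not govern whether a scan is done.

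Pre-dose does not mean untreated: children already on a chelator continue it until day −6, so a scan between day −20 and day −7 is made on prior therapy. That also stands, but prior therapy cannot depend on the assigned arm.

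A reader might infer three stronger points that the documents do not support.
- *Children who stop early are harmed by a late baseline window.* They are outside PP1 for want of a one-year value and are failures by rule (Sections 9, 11.2, 11.6 and 11.13), whatever the baseline timing.
- *A T2* below 10 ms will be discovered only after randomisation.* Scans are allowed from day −20, and Section 5.2 speaks of "cardiac MRI T2* lower than 10 ms available", which reads naturally as an existing result. Eligibility is settled at V2, day −7 (Section 7.3.3), so even a pre-dose scan in the last week would come after that decision. This is an ambiguity to reconcile, not a breach.
- *The 325-to-405-day spread (ratio 1.25) swamps a 10% threshold.* Days elapsed and percentage change in T2* are different quantities. Much of the spread comes from the month-12 window, which is reasonable to keep.

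**Conclusion.** The contradiction is in the text: Section 7.2.1 requires the baseline scans before randomisation and first dose, and also permits them up to day +20. The on-treatment effect is minor, about 0.5% of T2* for a 10% annual gain under a linear assumption. It is similar in size to the effect of an early month-12 scan and matters only near the cut-offs.

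The more important part is that, for children aged 10 or over who complete the year, the existence of a baseline scan or the ferritin-only classification can be decided with the arm known. A reader might infer from the sensitivity table that the type I error is in fact inflated. The documents do not show that: they give no missing shares, the one-arm patterns are worst cases, and the table concerns the corroborating ITT analysis. It shows only that a small imbalance would matter. The point covers children due a cardiac scan and the secondary liver endpoint; baseline ferritin has no such window.

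**What to change.** - Require the baseline liver and cardiac MRI after consent and before randomisation and first dose, between day −20 and day 0, within the existing 28-day run-in. Keep the 20-day tolerance for months 6 and 12.
- Record before allocation whether each child aged 10 or over can be scanned without sedation, and use that record to fix which endpoint definition applies.
- Flag any baseline scan made after first dose, and add a sensitivity analysis excluding those children.
- Bring Section 7.2, Table 5 footnotes 3 and 4, the tolerance sentence in Section 7.2.1, and Sections 7.3.11 and 7.3.14 into line with the pre-dose rule in Section 7.2.1.
- Reconcile with the scan timing the two places that use T2* at entry: the exclusion in Section 5.2 and the initial-dose provision in Section 6.2, which refers to T2* although the scan may come after day 0. Which clinical rule should apply is for the sponsor and investigators to settle.

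The number of scans and the sample size do not change. The cost is tighter booking. Consent may come as late as day −8, and no study-specific assessment may precede it, which would leave about eight days. Booking will be hardest for those children and for children referred to another MRI centre. Reports are due within two working days, so a scan late in the run-in can be done in time even if its report arrives after day 0.

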7.2.2 On-Study/On-Intervention evaluations

V4/month 1, V5/month 2, V7/month 4, V8/month 5, V10/month 7, V11/month 8, V13/month 10, V14/month 11 assessments

CONFIDENTIAL

DEEP Consortium
DEEP2-Efficacy/Safety Study Protocol

Protocol No. DEEP-2

These visits will be completed on the same calendar day (± 7 days) of the appropriate month as the baseline evaluation.

At each visit the following assessments will be performed:

- Clinical physical examination
- Vital signs
- Serum ferritin
- Urinalysis
- Renal function
- Haemoglobin
- Neutrophil count
- Haematology/Biochemistry
- Concomitant medications
- Adverse events
- Body height/weight
- Compliance
- Healthcare resources

Additional information regarding clinical procedures will be provided in the SPM.

V6/month 3 assessments

These visits will be completed within the same calendar day of the month (± 7 days).

At each visit the following assessments will be performed:

- Clinical physical examination
- Vital signs
- Serum Ferritin
- ECG
- Urinalysis
- Renal function
- Haemoglobin
- Neutrophil count
- Haematology/Biochemistry
- Concomitant medications
- Adverse events
- Body height/weight
- Compliance
- Healthcare resources

Additional information regarding clinical procedures will be provided in the SPM.

V9/month 6 assessment

This visit will be completed within the same calendar day of the month (± 7 days).

The following assessments will be performed:

- Clinical physical examination

- Vital signs
- Serum Ferritin
- ECG
- Cardiac MRI T2*
- Urinalysis
- Renal function
- Haemoglobin
- Neutrophil count
- Haematology/Biochemistry
- Concomitant medications
- Adverse events
- Body height/weight
- Pubertal staging (according to Tanner, see **Section 10.1**)
- Compliance
- CHQ
- Healthcare resources

Additional information regarding clinical procedures will be provided in the SPM.

V12/month 9 assessments

These visits will be completed within the same calendar day of the month (± 7 days).

At this visit the following assessments will be performed:

- Clinical physical examination
- Vital signs
- Serum Ferritin
- ECG
- Urinalysis
- Renal function
- Haemoglobin
- Neutrophil count
- Haematology/Biochemistry
- Concomitant medications
- Adverse events
- Body height/weight
- Compliance
- Healthcare resources

Additional information regarding clinical procedures will be provided in the SPM.

7.2.3 On-Study/Off-Intervention evaluations

This visit will occur only if the patient withdraws consent or the investigator identifies medical reasons to withdraw the patient from the study. In this event, all the assessments included in the V16/ follow up assessments will be conducted.

7.2.4 Final On-Study evaluations**V15/month 12 assessment**

This visit will be completed within the same calendar day of the month (± 7 days) and constitutes the final on treatment evaluation.

The following assessments will be performed:

- Pregnancy test
- Clinical physical examination
- Pharmacokinetics
- Vital signs
- Liver MRI
- Serum Ferritin
- ECG
- Cardiac MRI T2*
- Urinalysis
- Renal function
- Haemoglobin
- Neutrophil count
- Hepatitis serology
- Haematology/Biochemistry
- Concomitant medications
- Adverse events
- Body height/weight
- Ocular examination
- Audiometric examination
- Pubertal staging (according to Tanner, see **Section 10.1**)
- Compliance
- CHQ
- Healthcare resources

On this visit day, the treatment drug should be administered in the clinic under supervision of qualified staff and time recorded accordingly. Accurate assessment of the pharmacokinetics of DPF and DFX will require that blood sampling and time of last dose administration will be recorded.

Additional information regarding clinical procedures will be provided in the SPM.

7.2.5 Off-Study requirements**V16/month 13 follow up assessment or withdrawal visit**

CONFIDENTIAL

DEEP Consortium
DEEP2-Efficacy/Safety Study Protocol

Protocol No. DEEP-2

This visit should be completed one month (\pm 7 days) after Visit 15 or in case of withdrawal. The following assessments will be performed:

- Clinical physical examination
- Vital signs
- Concomitant medications
- Adverse events
- Body height/weight

In case of withdrawal, centralized serum ferritin and CHQ will be also assessed.

Additional information regarding clinical procedures will be provided in the SPM.

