7. CLINICAL AND LABORATORY EVALUATIONS

7.1 Study outline

This study includes: a run-in period (maximum 28 days), a 12 months treatment period and a follow-up visit 1 month after last administration, as detailed below in **Figure 1**.

Figure 1: Study outline

The study procedures and outline develop as follows:

- Run-in period (day -28 to -1) divided in:
 - *Screening period* (day -28 to -7): Patients on their standard chelator schedule will be screened for eligibility. Two visits are foreseen in this period, the first one (Visit 1, between day -28 and day -8) to describe the study to the patient and to his/her parents and to obtain the informed consent, the second one (Visit 2, day -7) to assess the inclusion/exclusion criteria (see **Section 5.1** and **Section 5.2**)

- *Washout period* (day -6 to -1): At day -6 patients will discontinue their ongoing chelator to start the washout phase.

The recruitment will start with the first eligible patient having signed informed consent and will continue for 12 months or less if the required number of patients has been reached.

- Treatment and observation period (month 1-month 12): the treatment period will start on Day 0 during V3 with randomization and will continue for 12 months. Patients will be visited every month. At each visit, assessments as detailed in **Table 5** will be conducted with a constant attention to the minimisation of pain and distress to the patient.

Ferritin levels for efficacy assessments will be evaluated quarterly (centrally). Additionally, ferritin levels for patient's medical management will be evaluated monthly (locally).

Cardiac MRI T2* in patients above 10 years of age able to undergo the MRI evaluation without sedation (regardless of their assignment treatment) will be assessed at baseline (V3), at month 6 (V9) and at the end of treatment (month 12, V15).

Liver MRI will be assessed in all patients able to undergo the MRI evaluation without sedation (regardless of their assigned treatment) at baseline (V3) and at the end of treatment (month 12, V15).

Patients will continue with their regular transfusional regimen.

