7.3.16 Renal function

Renal function will be assessed as serum creatinine and creatinine clearance calculated according to Schwartz formula. Both parameters will be determined at each scheduled study visit (V1 to V15) and weekly (\pm 7 days) during the first month after initiation or modification of therapy.

Serum creatinine for checking exclusion criteria must be assessed in duplicate between day -9 and day -7 of the screening period.

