9. INTERRUPTION OF TREATMENT

This section deals with a patient's premature withdrawal from the study before completing all scheduled visits. An individual subject may be withdrawn at the discretion of the responsible investigator and the study team for the reasons listed hereby. In the event one or more subjects are withdrawn, additional subjects may be enrolled to ensure an adequate number of subjects complete the cohort.

Reasons that a patient must discontinue participation in a clinical study are considered to constitute one of the following:

1. unsatisfactory therapeutic effect (quarterly increase in ferritin levels of at least 1500 ng/ml as detected by two determinations performed at no more than two weeks interval, or if cardiac MRI T2* decreases under 10ms)
2. subject's condition no longer requires study treatment
3. DFX treatment at 10 mg/kg/day (for safety reasons) for more than 4 weeks
4. DFP or DFX administration suspended (for safety reasons) for more than 4 weeks
5. adverse event(s) requiring change of chelation therapy, including moderate or severe Neutropenia
6. significant protocol violation
7. subject/legal guardian withdrew consent/assent
8. lost to follow-up
9. administrative problems
10. death

In the absence of a medical contraindication or significant protocol violation, the investigator may make an effort to keep the subject in the study. Should a subject withdraw or be withdrawn by the legal guardian, he/she has to complete a full set of the 'end-of-study phase assessments', i.e. a full V16 evaluation. Relevant records will have to be done on the corresponding CRF pages.

This requirement does not refer to patients who passed the screening and washout period and were found not to be eligible for treatment.

Patients prematurely withdrawn from the treatment will be considered treatment failures.

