16. ADVERSE EVENTS (AE) AND SERIOUS ADVERSE EVENTS (SAE) REPORTING

According to ICH E6 Guideline (Good Clinical Practice, GCP), both Investigators and Sponsor follow specific procedures when notifying and reporting adverse events/reactions in clinical trials.

The Principal Investigator or qualified site staff is responsible for detecting, documenting and reporting events that meet the definition of an AE or SAE.

AEs will be collected from the start of Investigational Product and until the follow-up contact. Medical occurrences that begin prior to the start of investigational product but after obtaining informed consent should be recorded separately from the Medical History/Current Medical Conditions CRF.

SAEs will be collected over the same time period as stated above for AEs. However, any SAEs assessed as related to study participation (e.g. investigational product, protocol-mandated procedures, invasive tests, or change in existing therapy) will be recorded from the time a subject consents to participate in the study up to 30 days from last dose or study related invasive procedure. All SAEs will be recorded and reported to Safety Contact (SC) within 24 hours after the Investigator has become aware of the event, as indicated in Section 16.3.

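### V16 doubles as the one-month follow-up and the withdrawal visit with no stated interval from last dose, so early leavers may have shorter AE collection than Section 7.1 implies, and the withdrawal laboratory lists disagree

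*Combined protocol and SAP*

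**What the plan says.** Section 7.1 describes "a 12 months treatment period and a follow-up visit 1 month after last administration", with no restriction to patients who finish treatment. Section 7.2.5 heads V16 as either the month 13 follow-up or the withdrawal visit and times it one month (±7 days) "after Visit 15 or in case of withdrawal. The following assessments will be performed". Section 7.2.3 says that when a patient withdraws, "all the assessments included in the V16/ follow up assessments will be conducted". Section 9 asks the withdrawn patient for the end-of-study assessments, "i.e. a full V16 evaluation". None of these sections describes a later contact.

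On collection periods, Section 16 states that "AEs will be collected from the start of Investigational Product and until the follow-up contact", and applies the same period to SAEs in general. SAEs related to study participation have a longer period, from consent "up to 30 days from last dose or study related invasive procedure".

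On tests at withdrawal, Section 7.2.5 says "In case of withdrawal, centralized serum ferritin and CHQ will be also assessed". Table 5 footnote 10 names central ferritin, the CHQ and also haematology/biochemistry. Section 7.3.20 likewise includes haematology/biochemistry at the withdrawal visit.

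**The concern.** A completer takes the last dose at V15 and is seen about a month later. A patient who stops early can use up V16 at the moment of stopping, and under Section 16 that visit can be read as the end of AE collection. The two groups then have different post-dose observation. The shorter one falls on patients who leave, some of them because of an adverse event. Safety and tolerability form the fourth secondary objective in Section 2.2, and Section 11.7 summarises AEs as numbers and percentages of patients per arm without mentioning observation time, so a shorter collection period would not show in the tables.

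The laboratory conflict is simpler: a site that follows Section 7.2.5 as written would omit tests that two other parts of the protocol require.

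**Working it through.** **Step 1. Post-dose collection for a completer.** The last dose is given in clinic at V15 (Section 7.3.7). V16 follows one month ±7 days later (Section 7.2.5), and AE collection ends there (Section 16). That gives about one month.

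**Step 2. Post-dose collection for an early leaver.** V16 is the withdrawal visit. Let g be the time in months from last dose to that visit. The protocol does not give g. Section 7.3.12 refers to an early termination visit, and Section 7.3.4 counts 30 days of contraception from early termination or from V16 as alternatives. Both suggest a visit at stopping, but neither fixes it. I therefore take g from 0 to 1 as an assumption.

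**Step 3. What falls in the gap between g and one month.**
- New non-serious AE: collection has ended.
- New SAE not judged related: collection has ended, because SAEs in general share the AE period.
- New related SAE: still due to 30 days after last dose, but no contact is scheduled to find it.
- SAE already reported: followed until recovered or stable (Section 16.4), so not lost.
- Moderate or severe neutropenia leading to withdrawal: monitored until resolution (Section 7.3.18), so not lost.

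**Step 4. Size.** Inputs from Section 11.12: 310 evaluable patients and about 20% dropout. The plan's enrolment figure reproduces: 310 / (1 − 0.20) = 387.5, rounded up to 388.

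Planned dropouts: 388 − 310 = 78 (0.20 × 388 = 77.6), or 39 per arm if equal.

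Patient-months of post-dose collection lost = 78 × (1 − g). One month for everyone would give 388 patient-months.
- g = 0: 78, or 78 / 388 = 20%
- g = 0.25: 58.5, or 15%
- g = 0.5: 39, or 10%
- g = 0.75: 19.5, or 5%
- g = 1: 0

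If dropout were 10% or 5% (assumed), the patients concerned would be 0.10 × 388 ≈ 39 or 0.05 × 388 ≈ 19.

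**Step 5. Withdrawal tests, side by side.**
- Section 7.2.5: central ferritin and CHQ, added to the V16 list, which contains no blood or urine test.
- Table 5 footnote 10: central ferritin, haematology/biochemistry and CHQ.
- Section 7.3.20: haematology/biochemistry at the withdrawal visit.

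The first conflicts with the other two. None of the three names renal function or urinalysis. The Table 5 rows for those tests could not be read in the copy available, so any mark there for withdrawal cannot be checked.

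**The case against.** The strongest reply is that Section 7.1 already sets the follow-up one month after last administration for everyone, and that Section 7.2.5 does not say the withdrawal visit takes place on the day of stopping. On that reading nothing is lost. This stands as far as it goes: the loss depends on how sites apply the text, which is why the range starts at zero. It does not remove the conflict, because no section tells a site to hold a second contact once V16 has been used.

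A reader might infer several stronger points that the documents do not support.
- *Early leavers lose all post-dose AE collection.* They do not. Related SAEs are due to 30 days after last dose for every patient, reported SAEs are followed until recovered or stable, and moderate or severe neutropenia is monitored to resolution. Patients withdrawn because dosing was suspended for more than four weeks (Section 9, reason 4) have already passed the window.
- *Neutropenia or creatinine changes after stopping would be missed because of the shared visit.* The listed V16 has no laboratory tests for completers either, so this is not a difference created by withdrawal.
- *Renal tests are planned only to V15.* Section 7.3.16 says "Both parameters will be determined at each scheduled study visit (V1 to V15", but the sentence goes on to add weekly tests in the first month after starting or modifying therapy. Section 7.3.15 does the same for urinalysis. Whether permanent stopping counts as modification is not stated.
- *The comparison between arms is biased.* Withdrawal reason 3 and the renal dose rules of Table 4 act on DFX only, so unequal withdrawal is plausible. The documents give no dropout rate by arm, and Section 11.7 uses any safety tests only to flag comparisons for further consideration. A bias of a given size or direction cannot be derived.

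**Conclusion.** The point holds as a conflict over visit timing, AE collection and withdrawal tests. Sections 7.2.3, 7.2.5 and 9 let one visit serve two purposes, which does not fit Section 7.1 and, through Section 16, can end AE collection early for patients who leave. What is exposed is limited to new non-serious AEs, new SAEs not judged related, and related SAEs that have a reporting duty but no scheduled contact.

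The size is at most about 78 of 388 patients and 0 to 78 patient-months. This rests on the planned 20% dropout and on an unstated interval between last dose and withdrawal visit. The 78 is a ceiling at that dropout rate: it counts every dropout as having a withdrawal visit, although patients already off drug for more than four weeks, lost to follow-up or deceased are not affected. The primary endpoint, its analysis and the sample size do not change.

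The haematology/biochemistry conflict is plain from the text. The status of renal function and urinalysis at withdrawal is unclear rather than shown to be missing.

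**What to change.** - Separate the withdrawal visit from the follow-up in Sections 7.2.3, 7.2.5, 9 and Table 5.
- Hold the follow-up one month (±7 days) after last dose for every treated patient, as Section 7.1 states, by visit or by contact if the family declines a visit.
- In Section 16, define the end of AE collection as that follow-up and not before 30 days after last dose.
- Reconcile Section 7.2.5 with Table 5 footnote 10 and Section 7.3.20 on haematology/biochemistry, and state there whether renal function and urinalysis belong to the withdrawal assessments.

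The cost is protocol wording, a CRF page and one extra short contact for up to about 78 patients. Some will decline, and those who have withdrawn consent may not be reachable, so the follow-up will not be complete.
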